2.1 General Design

This will be a prospective 1:1 randomized controlled trial with the following study arms:

Arm 1: Patient Group 1

Standard Care Only. Patients will undergo intra-operative bile aspiration (as is routinely performed) with SC of the aspirate. All patients will receive standard prophylactic antibiotics according to practice standards and will be continued for up to 5 days as is routine. If bile cultures are positive, antimicrobials will be continued for a complete 10-day course of antibiotics (Figure 2).

Arm 2: Patient Group 2

Standard Care + ONT. Patients will undergo intra-operative bile aspiration (as is routinely performed) with standard cultures AND ONT sequencing of the aspirate. All patients will receive standard prophylactic antibiotics according to practice standards. ONT sequencing results will be made available to providers through electronic medical record (EMR) and team electronic notifications. Patients with negative ONT results will be taken off the standard prophylactic antibiotics and patients with positive ONT results will have antimicrobial therapy adjusted according to ONT sequencing results. However, if SCs are positive or suggest alternative/broader coverage then these results

will guide therapy and not ONT results. If bile cultures are positive, antimicrobials will be continued for a complete 10-day course of antibiotics (Figure 2).

[figure not shown]

Figure 2: A schematic diagram of our proposed study to investigate the use of Oxford nanopore sequencing to detect and characterize biliary microbial contamination

The study will include patients undergoing elective pancreaticoduodenectomy or total pancreatectomy for any clinical indication. Patients will be excluded from the study if they are < 18 years of age, enrolled in any similar clinical trials involving use of peri-operative antibiotics, are undergoing distal pancreatectomy, or undergoing emergency total pancreatectomy or emergency pancreaticoduodenectomy (Table 4). Following recruitment to the study, patients will be randomly assigned intraoperatively/post-operative to either the control group (Arm 1) or the interventional group (Arm 2). We will use stratified randomization with age (below 65 years vs 65 years and above), sex, operation type (pancreaticoduodenectomy vs total pancreatectomy), biliary stenting (yes vs no), and patient ASA score as stratification factors.

Table 4: Patient inclusion and exclusion criteria for the clinical trial

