Inclusion Criteria	
 • > 18 years of age • Scheduled for elective total pancreatectomy or pancreaticoduodenectomy
Exclusion Criteria	
 • < 18 years of age

	
• Emergency total pancreatectomy or pancreaticoduodenectomy• Patients scheduled for distal pancreatectomy• Women who are pregnant• Patients without the cognitive capacity to consent• Patients enrolled in similar clinical trials involving use of perioperative antibiotics
--	--

Bile will be collected via bile duct aspiration. Bile aspiration will be performed with a 16-gauge needle and 3 cc syringe prior to bile duct division (Figure 3), and aspirated material will be aseptically transferred into sterile aerobic and anaerobic transport vials. Samples will be concurrently transported to the Pathology lab and the microbiome lab to undergo SC techniques and ONT sequencing, respectively. Standardization of bile collection and surgical procedure will be assured as all surgeries will be performed by the same lead surgeon, [name]. Surgical variables that have been associated with increased SSI risk will be recorded. This will include patient sex, age, BMI, ASA score, the volume of blood loss, whether the patient had a biliary stent inserted prior to surgery, closure technique, and whether vascular reconstruction was performed during surgery.

[figure not shown]

Figure 3: Collection of intraoperative bile aspirate during pancreatic head resection (total pancreatectomy, pancreaticoduodenectomy)

SCs obtained from intraoperative bile aspiration for both study arms will be performed in compliance with clinical standards. This is routinely performed by the Pathology lab and no changes to these protocols are necessary (see Supplementary Materials S1 – S6) for culture methods and AST protocols). Results will be reported in the EMR which will be accessible by the clinical team, as is the current clinical practice. ONT sequencing for those assigned to Study Arm 2 will be performed on a 1cc liquid bile sample collected fresh from the operating room after specimen release from the Pathology lab. Approval from our institutional TRAG

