4.1 Description

Please refer to the manufacturing information/instructions for use provided by Oxford Nanopore Technologies for full device description. Briefly, the GridION MK1 is a ONT sequencing device that will be used to examine microbial DNA in bile cultures from subjects undergoing pancreatic head resection. The same GridION instrument (device ID GXB03025)

will be used to test each sample. Serial number/lot number information for the sterile, single time use flow cells/ reagents will be recorded on a device accountability log. MinKnow, Guppy, Porechop, BBMap, Centrifuge, and ResFinder 4.1 software will be used for data analysis. The GridION device will be stored in a secure laboratory and only be accessible to trained study staff. In the event the GridION needs replacement, we will contact the manufacturer for a replacement and validate performance using residual DNA from our published studies. A GridION instrument will be considered validated if microbial species are detected in the expected proportions. We will then record the new GridION serial number and date put into service for this study.

ONT sequencing and analysis will only be performed by our Postdoctoral Fellow trained in the technology, and there are no medical or surgical procedures involved in the use of the device

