6.2 Statistical Methods

Descriptive Statistics

The primary analysis of this study will be a modified intention to treat analysis (ITT), performed to determine how use of ONT changed patient treatment, i.e. did use of ONT improve antibiotic stewardship. Proportions of patients with detection of microbes of interest will be estimated along with exact 95% binomial confidence intervals. Comparisons of the proportions between the two study arms will be compared using Fisher's exact test or Chi-square test as appropriate. We will calculate the time from randomization to first microbial detection within a patient. We will report the mean difference in time to first microbial detection within 96 hours post randomization in both treatment arms, together with a 95% confidence interval. Comparison of time to first microbial detection within 96 hours post randomization, will be performed using Wilcoxon rank sum test or two sample t-test as appropriate. If there are any baseline imbalances in demographic or clinical variables between the two groups, we will perform the analysis using univariable and multivariable linear regression adjusting for these variables with imbalances as possible confounders. Duration of antibiotics, total number of different antibiotics, and broad-spectrum antibiotics vs narrow-spectrum antibiotics administered in the two arms will be compared to determine if use of ONT improved antibiotic stewardship by significantly reducing the duration of perioperative antibiotics and use of broad-spectrum antibiotics

Secondary analysis will evaluate SSI's will be evaluated and classified using ACS NSQIP definitions and data collected will include mortality rate, SSI incidence rate, ICU length of stay, total length of hospital stay, need for interventional procedures, and hospital readmission. Statistical analysis will be performed by the study team to determine if use of ONT significantly improved patient outcome compared to patients who received standard of care

only. The secondary endpoint of the study is a binary endpoint i.e. whether patients develop SSI (yes, no). Association between the secondary outcome and predictor variables will be assessed using univariable and multivariable logistic regression.

In both primary and secondary analysis, the following variables will be assessed for inclusion in the regression models

- Age at time of surgery DOB
- BMI at time of surgery RAVE calculate
- Sex

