Missing data could arise from lost samples or from a catastrophic failure of computer storage and backup systems. If any of these were to occur before an intervention could be determined using ONT sequencing, we will note these events and revert the patient to Standard of Care group.

Primary Hypothesis:

The use of ONT sequencing, a novel metagenomic technique, will result in more rapid identification of organisms in intra-operatively collected bile samples and allow for earlier treatment of biliary microbial contamination. Supplementing SC with ONT sequencing data will allow patients to be treated earlier in the post-operative setting with tailored antibiotics, which will reduce the rate of biliary microbial contamination related SSIs in patients undergoing pancreatic head resection as compared to standard cultures alone and will improve antimicrobial stewardship by avoiding unnecessary use of antibiotics.

7 Safety and Adverse Events

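### The missing-data rule can be read as moving Arm 2 patients without a sequencing result into the control group, and the undefined modified ITT does not prevent it

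*Combined protocol and SAP*

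**What the plan says.** The only missing-data rule is in Section 6.2 under Handling of Missing Data. It names two causes: "Missing data could arise from lost samples or from a catastrophic failure of computer storage and backup systems". It then sets the timing, "If any of these were to occur before an intervention could be determined using ONT sequencing", and the action: "we will note these events and revert the patient to Standard of Care group".

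Four other places bear on how that rule works.

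- **Analysis population (6.2):** "The primary analysis of this study will be a modified intention to treat analysis (ITT), performed to determine how use of ONT changed patient treatment". The modification is not defined here or elsewhere, and no text says that patients are analysed in the arm to which they were randomised.
- **Who is sequenced (2.1 General Design):** "ONT sequencing for those assigned to Study Arm 2 will be performed on a 1cc liquid bile sample".
- **When patients are randomised (2.1 General Design):** during or after the operation. The same section calls Arm 1 the control group and labels it Standard Care Only.
- **What is tested (2.2 Primary Objective):** better antibiotic stewardship through giving the surgical team rapid ONT data.

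**The concern.** The rule stands in the statistical plan and speaks of a *group*, which is the word the protocol uses for its arms. Read that way, it reassigns patients after randomisation because of an event that matters only in Arm 2, and the movement can go in one direction only. An ITT analysis would normally block this, but a modified ITT with no stated modification does not.

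The comparison of the arms as randomised is at stake. A lost sample is part of what happens when a hospital adopts the ONT strategy, and it leaves the patient on the standard course. If such patients leave Arm 2, the trial estimates the effect of ONT when a result arrives and reports it as the effect of offering ONT. The trial is also open-label (4.3), and 6.2 has the study team carry out the outcome analysis. A rule that can be read two ways therefore leaves arm membership to be decided after outcomes are known.

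**Working it through.** **Inputs.** From the documents: 70 per arm, 66 per group before rounding up, 54% and 77% positivity, alpha 0.05 and power 80% (6.1); preliminary SSI rate 21.4%, 9/42 (1.4). Assumed, because the documents give no figure: the failure proportion f in Arm 2, and the SSI risk of patients whose ONT result is lost.

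**1. Antibiotic duration.** Let D be the mean difference from standard care among sequenced patients. Suppose patients without a result receive standard care and do not otherwise differ.

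- As randomised: (1−f) × D + f × 0 = (1−f)D.
- As moved: the enlarged control group still has the standard-care mean and the remaining Arm 2 is all sequenced, so the difference is D.
- Ratio: D / [(1−f)D] = 1/(1−f).

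| Arm 2 without a result (assumed) | 1/(1−f) | Inflation |
|---|---|---|
| 1 of 70 | 70/69 = 1.014 | 1.4% |
| 2 of 70 | 70/68 = 1.029 | 2.9% |
| 5% | 1/0.95 = 1.053 | 5.3% |
| 10% | 1/0.90 = 1.111 | 11.1% |
| 20% | 1/0.80 = 1.250 | 25.0% |

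This inflation needs no link between failure and outcome.

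**2. The plan's own power basis.** The two-sided normal approximation without continuity correction, for 54% vs 77%, gives

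n = [1.960 × √(2 × 0.655 × 0.345) + 0.842 × √(0.54 × 0.46 + 0.77 × 0.23)]² / 0.23² = 65.9, or 66 per group.

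This reproduces the stated figure; power at 70 per arm is 82.4%. Now let k of the 70 Arm 2 patients have no ONT result and take the standard-culture rate of 54%. As randomised, the Arm 2 rate is (1−k/70) × 77% + (k/70) × 54%.

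| k | As randomised: difference, power (70 vs 70) | As moved: groups, difference, power | Per arm for 80% as randomised |
|---|---|---|---|
| 2 | 22.3 points, 79.9% | 72 vs 68, 23 points, 82.3% | 71 |
| 4 | 21.7 points, 77.2% | 74 vs 66, 23 points, 82.1% | 75 |
| 7 | 20.7 points, 72.9% | 77 vs 63, 23 points, 81.8% | 83 |
| 14 | 18.4 points, 61.9% | 84 vs 56, 23 points, 80.4% | 107 |

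When patients are moved, the contrast stays at 23 points whatever the failure rate, so the cost of failures drops out of the comparison. Positivity is not the antibiotic-use endpoint, so this table shows the mechanism only.

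**3. SSI, if failures are prognostic.** Assume no true effect, 21.4% SSI in both arms, 7 of 70 failures and a 40% SSI risk in those 7.

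- Remaining Arm 2: (0.214 − 0.10 × 0.40)/0.90 = 19.3%.
- Enlarged control group: (70 × 0.214 + 7 × 0.40)/77 = 23.1%.
- Spurious benefit: 3.8 points.

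For 4 to 14 failures at an assumed risk of 30 to 40%, the spurious benefit runs from 1.0 to 7.8 points. It is zero if the failed patients carry the average risk.

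**The case against.** The strongest reply is that the sentence is about care. It describes a patient for whom there is no ONT result to act on, and such a patient gets standard care in any case. Section 2.1 General Design uses the same verb for care when it lets clinicians revert to current practice if cultures grow. The phrase in 6.2 is also not the exact label of Arm 1. This stands in part: a reader might infer that the plan certainly breaks randomisation, and the documents do not support that. They leave the question open.

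A reader might also infer that the plan hides the failure rate. It does not. The same sentence says that the events will be noted, and 5.3 captures all ONT results, so the count can be recovered. What would be lost is the effect of failures on the between-arm estimate.

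A third tempting step is to apply the rule to every failed or late run and to argue bias from scant bile or from reliance on a single operator (4.1: "ONT sequencing and analysis will only be performed by our Postdoctoral Fellow trained in the technology"). The text names only lost samples and storage or backup failure. Other failures have no rule at all, and nothing in the documents ties the named events to prognosis. The SSI example is therefore conditional.

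Finally, some losses could come before allocation, because 5.2 describes bile pick-up before it mentions randomisation and assignment may be post-operative. The one-way argument applies to losses after allocation.

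None of these replies supplies the missing statement of where a reverted patient is counted.

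**Conclusion.** The point holds as an open risk to the primary analysis population. Followed literally as a data rule, the sentence moves randomised Arm 2 patients into the control group, and the undefined modified ITT does not stop it. If only care was meant and patients are analysed as randomised, there is no breach.

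The size depends on a failure rate that the documents do not give. For the narrow causes named, 1 or 2 losses in 70 would inflate the duration effect by about 1 to 3%, which is small. Failures of 5 to 20% would inflate it by about 5 to 25%, even when unrelated to outcome. Bias in SSI needs the further assumption that failed patients differ in risk; the 3.8-point example rests on an assumed 40% SSI risk in an assumed 10% of Arm 2.

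**What to change.** Leave the clinical handling as it is and add the analysis rule that is missing from 6.2:

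- State that every randomised patient is analysed in the assigned arm, whether or not an ONT result is available and whatever the reason. This also covers failed runs, insufficient DNA and late results, which now have no rule.
- Drop *modified*, or define it so that no patient leaves the assigned arm.
- Report the number, cause and timing of missing ONT results in Arm 2, with the proportion and an exact 95% confidence interval.
- Keep any analysis restricted to sequenced patients as a labelled sensitivity analysis.

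The cost is a few sentences and no new data items. The downside is that the estimated effect shrinks by the factor (1−f), and power falls with it. On the plan's positivity basis, 7 of 70 failures would leave 72.9% power at 70 per arm, and 83 per arm would be needed for 80%. If failures are expected to be more than rare, the target of 140 should be reconsidered at the same time.

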9.3	CASE REPORT FORMS	22
9.4	RECORDS RETENTION	23
10	STUDY MONITORING, AUDITING, AND INSPECTING	23
10.1	STUDY MONITORING PLAN	23
10.2	AUDITING AND INSPECTING	383
11	ETHICAL CONSIDERATIONS	38
12	STUDY FINANCES	394
12.1	FUNDING SOURCE	394
13	PUBLICATION PLAN	394
14	REFERENCES	24
15	ATTACHMENTS	26 ERROR! BOOKMARK NOT DEFINED.

LIST OF ABBREVIATIONS

AE	Adverse Event/Adverse Experience
CFR	Code of Federal Regulations
CRF	Case Report Form
DSMB	Data and Safety Monitoring Board
FDA	Food and Drug Administration
GCP	Good Clinical Practice
HIPAA	Health Insurance Portability and Accountability Act
ICU	Intensive Care Unit
IDE	Investigational Device Exemption
IRB	Institutional Review Board
NS	Nanopore Sequencing
PHI	Protected Health Information
PI	Principal Investigator
SAE	Serious Adverse Event/Serious Adverse Experience
SOP	Standard Operating Procedure
SSI	Surgical Site Infection
TRAG	Tissue Request Acquisition Group
UADE	Unanticipated Adverse Device Effect

Study Summary

Title	“Answers in Hours” A Randomized Controlled Trial Using Microbiome Metagenomics for Bile Duct Cultures
Running Title	“Answers in Hours”
IRB Protocol Number	21-004234
Phase	Pilot
Methodology	Randomized 1:1 Controlled Trial
Overall Study Duration	3 years
Subject Participation Duration	90 days
Objectives	
Reduce the rate of bacterobilia driven surgical site infection (SSI) in patients undergoing pancreatic head resection by providing surgical team with Oxford Nanopore (ONT) microbial sequencing data in the post-operative setting.
 
Reduce cost of care through reduction in SSI and improved antibiotic stewardship.

Number of Subjects	140
Diagnosis and Main Inclusion Criteria	Any adult, male or female, over age 18, undergoing pancreaticoduodenectomy or total pancreatectomy for benign or malignant indication.
Study Device	GridION Sequencing Instrument
Reference therapy	Standard culture techniques and prolonged peri-operative antibiotics
Statistical Methodology	For continuous variables, t-test will be performed and for binary variables chi-square or fisher's exact testing will be performed as appropriate. Universal and multivariable linear regression adjustment will be performed if any baseline imbalances in demographic or clinical variables are detected

1 Introduction

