1.6 Anticipated Duration of the Clinical Investigation

The anticipated duration of this study is 2 years. Direct participation for participants lasts until surgical specimens have been obtained. Additional follow-up data will be collected from the medical record for up to 90 days following the procedure.

2 Study Objectives

2.1 Hypothesis:

The use of ONT sequencing, a novel metagenomic technique, will result in faster identification of organisms from intra-operatively collected bile samples and allow for early treatment of biliary microbial contamination. Supplementing SC with ONT sequencing data will allow patients to be treated earlier in the post-operative setting with tailored antibiotics, which will reduce the rate of biliary microbial contamination related SSIs in patients undergoing pancreatic head resection as compared to SC alone.

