2.2 Primary Objective

To improve antibiotic stewardship (reducing duration of peri-operative prophylactic antibiotic regimen, reducing administration of broad-spectrum antibiotic) by providing surgical team with rapid ONT sequencing data in the early post-operative setting.

Success Criteria: Significantly reduced antibiotic regimen duration and use of broad-spectrum antibiotics, corrected for key co-variates ($p<0.1$).

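### The SSI claim in the Primary Hypothesis is not tested by the primary analysis, bile-related SSI is never defined, and the primary endpoint as worded would be failed by a significant fall in SSI

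*Combined protocol and SAP*

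**What the plan says.** **Where SSI reduction is the claim.** The paragraph headed Primary Hypothesis, at the end of section 6.2, has three parts. ONT sequencing "will result in more rapid identification of organisms in intra-operatively collected bile samples" and allows earlier treatment. This leads to tailored therapy, "which will reduce the rate of biliary microbial contamination related SSIs in patients undergoing pancreatic head resection as compared to standard cultures alone". The same sentence ends "and will improve antimicrobial stewardship by avoiding unnecessary use of antibiotics". Section 2.1 Hypothesis has the speed and SSI parts ("which will reduce the rate of biliary microbial contamination related SSIs in patients undergoing pancreatic head resection as compared to SC alone") but no stewardship part. The first of two unranked objectives in the Study Summary is "Reduce the rate of bacterobilia driven surgical site infection (SSI) in patients undergoing pancreatic head resection"; the second is lower cost through less SSI and better stewardship.

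**Where antibiotic use is primary.** Section 2.2 Primary Objective begins "To improve antibiotic stewardship". Section 5.3 lists duration, number and spectrum of antibiotics as the primary outcomes. Section 6.2 sets the primary analysis as a modified intention-to-treat comparison of whether ONT improved stewardship.

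**Where SSI is secondary.** The Secondary Objective and 2.3 Secondary Study Endpoints both list SSI reduction, and 6.2 says "The secondary endpoint of the study is a binary endpoint i.e. whether patients develop SSI (yes, no". SSI is classified by ACS NSQIP definitions, and Table 6 sorts it by anatomical depth. The Secondary Objective counts success as significantly lower SSI together with lower hospital cost, at p<0.1.

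**Where SSI must not differ.** Section 2.2 Primary Study Endpoints gives one endpoint: less antibiotic administration, with an effect on SSI that is not significant (p>0.05).

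**The concern.** The plan gives SSI three roles: the outcome that should fall, the outcome that should show no significant change, and a secondary outcome. They cannot all hold for the same data.

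Suppose the trial finds less antibiotic use and no significant SSI difference. That meets the primary endpoint, and it also leaves the SSI part of the Primary Hypothesis unsupported. Suppose instead that SSI falls with p<0.05. That supports the hypothesis and helps meet the Secondary Objective, but fails the primary endpoint as worded. The plan does not say which statement governs. In an open trial, the choice could be made after the results are seen.

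The SSI named in the hypotheses is a particular kind, related to bile contamination. No rule links an infection to the organisms found in bile, so the predicted outcome is not one that any analysis, primary or secondary, uses.

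**Working it through.** **1. Each part of the Primary Hypothesis set against the analysis**

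| Part | In 2.1 Hypothesis? | Analysed where | Level |
|---|---|---|---|
| Faster identification | Yes | 6.2, time to first microbial detection within 96 hours | In the primary-analysis paragraph |
| Better stewardship | No | 6.2, duration, number and spectrum of antibiotics | Primary |
| Fewer bile-related SSIs | Yes | Nowhere; any SSI is analysed in 6.2 | Secondary |

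Only the SSI part lies outside the primary analysis. In 2.1 it is the only clinical-outcome claim.

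**2. SSI result against the endpoint rules**

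| SSI result | SSI part of hypothesis | SSI condition in primary endpoint | SSI half of secondary criterion |
|---|---|---|---|
| Reduction, p<0.05 | Supported | Failed | Met |
| Reduction, p between 0.05 and 0.1 | Unclear | Met | Met |
| No significant difference, p>0.1 | Not supported | Met | Not met |

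**3. The plan's own sample size (section 6.1)**

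Inputs: 54% and 77% detection positivity, alpha 0.05, power 80%. Two-sided, pooled variance under the null, no continuity correction:

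n = [z(0.975)·√(2·p̄(1−p̄)) + z(0.80)·√(p1(1−p1)+p2(1−p2))]² / (p1−p2)²

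With p̄ = 0.655: (1.960×0.6723 + 0.8416×0.6523)² / 0.23² = 3.484/0.0529 = 65.9, so 66 per arm. The stated figure reproduces, and SSI plays no part in it.

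**4. What 70 per arm can show about SSI**

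Control rates: 21.4% (9/42, pilot SSI within 30 days, section 1.4); 26.2% (11/42, adding the two later pilot SSIs at days 34 and 42); 25% and 45% (the range cited in 1.5.1). The documents give no target reduction, so halving is an assumption used for scale.

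Power = Φ{[|p1−p2|·√n − z·√(2·p̄(1−p̄))] / √(p1(1−p1)+p2(1−p2))}

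For 21.4% to 10.7%: (0.1071×8.367 − 1.960×0.5194)/0.5138 = −0.237, and Φ(−0.237) = 0.41.

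| Control SSI rate | Power to halve, two-sided 0.05 | Power to halve, two-sided 0.10 |
|---|---|---|
| 21.4% | 41% | 53% |
| 25% | 47% | 60% |
| 26.2% | 50% | 62% |
| 45% | 81% | 89% |

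**5. Precision**

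With equal rates p in both arms, the 95% half-width for the difference is 1.96·√(2p(1−p)/70). This gives 0.136 at 21.4% and 0.146 at 26.2%, about 14 to 15 percentage points. An observed difference of zero at 21.4% would be compatible with a rise or a fall of about 14 points.

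**The case against.** A reader might infer that the primary analysis does not test the Primary Hypothesis at all. The documents do not support that. The hypothesis in 6.2 is compound, its stewardship clause is coordinate with the SSI clause, and nothing there ranks one above the other. The primary-analysis paragraph tests stewardship and speed. The fault is confined to the SSI part. It is sharper in 2.1, which has no stewardship clause, but 2.1 is not labelled primary. The Study Summary likewise does not rank its objectives.

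It can also be said that low power for a secondary outcome in a trial labelled a pilot is no defect, and that power does not measure a labelling mismatch. Both points stand. The power figures matter here for two narrower reasons: the hypothesis predicts an SSI reduction, and the primary endpoint treats non-significance as a favourable finding. Nor is power poor under every assumption. At 45%, the top of the cited range, halving SSI has 81% power. The pilot, however, gives 21% to 26%.

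Finally, the SSI condition in the primary endpoint may have been meant to say only that SSI should not get worse. That is plausible, but the text gives no direction and no margin, and p>0.05 would not establish it.

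**Conclusion.** Wrong as written, and it should be corrected. The SSI part of the Primary Hypothesis is not tested by the primary analysis, bile-related SSI is undefined and analysed nowhere, and the SSI condition in the primary endpoint conflicts with a hypothesis of SSI reduction. These conclusions rest on the text alone.

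The size of the interpretive problem depends on the control SSI rate. At the pilot rates of 21.4% to 26.2%, a true halving would be missed in about 50% to 59% of trials at 0.05, and the interval would extend about 14 to 15 points each side. At 45% the miss rate is about 19%. The figures assume a two-sided unadjusted comparison, 70 evaluable patients per arm and a halving of risk; the pilot counts may not equal the 90-day rate. Two further inferences go beyond the documents: that a null SSI result would refute the hypothesis, and that it would show that using fewer antibiotics is harmless. At this size it would show neither.

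**What to change.** - **Study Summary, 2.1 Hypothesis and 6.2 Primary Hypothesis:** state one primary hypothesis, on antibiotic use, matching the Primary Objective, 5.3 and the primary analysis.
- **SSI hypothesis:** make it secondary, on any SSI within 90 days. If the bile-related wording is kept, define how an infection is attributed to bile organisms and add it as an analysed outcome.
- **2.2 Primary Study Endpoints:** remove the condition that the SSI effect be non-significant.
- **2.2 Secondary Objective:** reconcile the p<0.1 success criterion with the revised secondary hypothesis. If it is left unchanged, it would contradict the reporting statement below.
- **6.1 and 6.2:** report SSI as a risk difference with a 95% confidence interval. State that 140 patients were not sized on SSI, give the expected interval width, and say that a non-significant result shows neither no benefit nor no harm.

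The cost is wording in the protocol and SAP. No patients, visits or procedures are added. The real concession is that the sponsor gives up SSI reduction as a primary claim.
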